4.8. Assessment time points

Visits for evaluation will be done in a blinded fashion with independent evaluators who will perform all follow-up evaluations. Patients will have all outcome measures on initial entry into the study (pre-treatment), at 4 weeks, 8 weeks, 12 weeks, 24 weeks and 52 weeks after entry into the study.

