4.3. Randomization

Blocked randomization will be used to assign to their respective treatment arm. The assigning ratio will be one to two; The random method of selection will be through a computerized random number generator. The on-site coordinator will be responsible for entering and maintaining the subject randomization information.

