4.9. Outcome measures

Primary study outcome:

- Western Ontario and McMaster Universities (WOMAC) pain scale at one year.
- WOMAC function scale at one year

Secondary study outcome: at: Pre-treatment, 4 weeks, 8 weeks, 12 weeks, 24 weeks, 52 weeks.

- WOMAC pain and function subscale
- PROMIS Pain Interference and Physical Function
- Costs: Assessment of total utilization and cost from resource utilization monitored via the CMO
- MOS item of the Short Form (SF)-36
- Spatio-temporal gait assessment including gait velocity, step length, single limb support and limb symmetry measured by Zeno Walkway ®
- 6-min walk test
- Blood pressure and resting heart rate

- Treatment adherence: Measured via attendance at sessions of therapy (conventional therapy), hours of use of AposTherapy (Patient to have step counter)
- Overall activity and sleep patterns (both arms (via FitBit Charge HR (<http://www.fitbit.com/chargehr#i.f9n1ye1ehxd30p>) motion sensor worn for one week after each evaluation session, mailed back via prepaid mailer at the end of the week.)

5. Statistical analysis

All demographic data will be reported as mean standard deviations and average. Data from primary and secondary outcome measures will be checked for skewness using Fisher-Pearson coefficient of skewness. ANOVA or Kuskal-Wallis test will be applied depending on normality of data. All statistical analysis will be conducted using IBM SPSS Statistics Ver.24.

6. Benefits

- Participants will all have physical therapy for their knee
- AposTherapy involves fewer visits to the physical therapy center thus allowing individuals more time at home and lower transportation costs
- AposTherapy is done at home and more convenient
- AposTherapy will be provided for free for participants.

7. Risks

- Muscle soreness associated with exercise
- Minimal fall risk with use of new footwear device and exercise

8. Subject Reimbursement

Participants will be reimbursed a total of \$40 at each assessment point (pre-treatment, at 4 weeks, 8 weeks, 12 weeks, 24 weeks and 52 weeks after entry into the study). Participants will

receive \$95 reimbursement for their time at the completion of the study after return of all devices and materials. This will apply to all arms of the study.

Study schedule:

Study Periods	Screening	1	2	3	4	5	6	7
Visit		1	2	3	4	5	6	7
Time (week)	-2	0	4	8	12	24	52	
Patient Information and Informed Consent	X							
Demographics	X							
Medical History	X							

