In- /Exclusion Criteria	X							
Radiography	X							
Randomization	X							
Administer traditional physical therapy		Physical Therapy is administered according to the protocol for the duration of enrollment in the study						
Administer Biomechanical Device		X						
Adjustment Biomechanical Device			X	X	X	X		
VAS and ODI		X	X	X	X	X	X	
Secondary outcome measures		X	X	X	X	X	X	
Adverse Events		X	X	X	X	X	X	

Resources

AposTherapy	Montefiore

 • Training for Montefiore PTs • Full-time Apos resource to manage program on-site at Montefiore • AposTherapy devices 	
 • Clinical Principle Investigator Lead • Research staff – 2 coordinators • Data informatics, including patient population, demographics, historical costs, etc. • Research infrastructure including IRB, recruitment, clinical expertise • Study materials • Step counter/Fitbit monitors

Staff	Salary - Rate/Hr	Fringe	FTE or Hours	Total Cost
Attending Physician Supervision	\$165,000	30.5%	0.2	\$43,065
Study coordinator	\$0	0.0%	2	\$0
These will be Everest individuals				
Informatics costs	\$75		100	\$7,500
Biostatistical support	\$150		100	\$15,000
CMO staff support	\$65,000	30.5%	0.5	\$42,413
Total Staffing Cost				\$107,978
Materials	Cost per Unit	# of Patients	Qty	Subject Costs
Step counters:				
25% of Patients and 10% loss	\$50	37	41	\$2,050
Fitbit HR Monitors:				
25% of Patients	\$150	37	41	\$6,150
Mailing to Recover step counter/Fitbit:*	\$10	37		\$14,800

Transportation costs:	\$100	147		\$14,700
Subject Complete Reimbursement	\$100	147		\$14,700
Zeno Walkway	\$20,000		1	\$20,000
Total Materials				\$72,400
Total cost of the study				\$180,378

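### The schedule randomises at week −2 but first takes baseline outcomes at week 0, and nothing withholds the arm until baseline is recorded

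*Combined protocol and SAP*

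**What the plan says.** The Study schedule table, after Section 8, has the time row "Time (week) -2 0 4 8 12 24 52". Two rows have their only mark in the Screening column (week −2): "In- /Exclusion Criteria X" and "Randomization X". The VAS and ODI row and the "Secondary outcome measures" row each have an empty Screening cell followed by six marks. The row "Administer Biomechanical Device" is marked in the same column as the first of those six.

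The table does not name WOMAC. Section 4.9 makes WOMAC pain and function at one year the primary outcomes, and also lists them among the secondary outcomes from pre-treatment onwards.

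On timing, Section 4.8 says "Patients will have all outcome measures on initial entry into the study (pre-treatment") and counts later visits from entry: "24 weeks and 52 weeks after entry into the study". The Synopsis counts the same visits from the start of treatment. Section 4.3 gives blocked, computer-generated randomisation in a 1:2 ratio and adds: "The on-site coordinator will be responsible for entering and maintaining the subject randomization information". It does not place randomisation relative to baseline or say when the arm is disclosed.

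Section 4.1 blinds the evaluator only. The Synopsis and Section 4.5 require a baseline VAS pain score of at least 3 cm. Section 5 names ANOVA or Kruskal-Wallis and gives baseline values no role.

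**The concern.** Baseline WOMAC and VAS are self-reported by patients who are not blinded. If they know their arm when they score, the scores can shift by arm through expectation or disappointment, and blinding the evaluator does not prevent this. A baseline that may already reflect the allocation is a poor reference for change scores and a poor covariate.

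Two further consequences follow from the printed order:

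- A patient randomised at week −2 who withdraws before week 0 would have no WOMAC score at all on this schedule.
- If the VAS entry criterion refers to the week 0 measurement, a patient scoring below 3 cm would be found ineligible after randomisation. The documents do not say how such a patient is handled, which leaves room for exclusions that differ by arm.

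**Working it through.** The plan gives no figure to reproduce on this point. The check is a reading of the schedule against the text, followed by a sensitivity calculation on assumed inputs.

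**1. Where the outcome rows start.** The time row has seven entries: −2, 0, 4, 8, 12, 24, 52. Each outcome row has six marks.

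- Starting at week 0, they fall at 0, 4, 8, 12, 24, 52, which are the six assessments in Section 4.8.
- Starting at Screening, they would fall at −2, 0, 4, 8, 12, 24, leaving week 52, the primary time point, empty.

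Only the first reading works. The header numbers seven visits for six post-screening times, but however it is aligned, the randomisation mark sits one column to the left of the first outcome mark. The gap is 0 − (−2) = 2 weeks.

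**2. Where WOMAC falls.** Through Section 4.9, WOMAC belongs to the secondary outcomes row, first marked at week 0. It is not an entry criterion, so the week −2 eligibility check cannot be read as covering it.

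**3. Whether the text restores the order.**

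- Section 4.8 orders baseline before treatment only. If entry means Screening, it disagrees with the schedule. If entry means week 0, baseline follows randomisation.
- Section 4.3 names who keeps the randomisation information, not when the arm is released.
- Section 4.7 has the device calibrated at the first assessment, so the arm must be known during that visit for device patients. Apart from the word pre-treatment, nothing orders baseline scoring against disclosure within it.

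**4. The VAS criterion.** Eligibility is marked at week −2 and VAS first appears at week 0. If baseline means week 0, eligibility is settled after randomisation. If a VAS is also taken at the screening check, that problem does not arise, but the table does not show it and the wording still needs reconciling.

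**5. Sensitivity.** Let d be a shift in mean baseline WOMAC pain in one arm caused by knowing the allocation, and b the slope of the one-year score on baseline. Neither is in the documents. I assume d = 0.1 to 0.5 on the 0–10 scale and b = 0.3 to 0.7. The target difference of 1.5 is from Section 4.6. The estimated arm difference moves by:

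| Analysis | Size of movement | Low | High | As % of 1.5 |
|---|---|---|---|---|
| Change score | d | 0.1 | 0.5 | 0.1/1.5 = 6.7% to 0.5/1.5 = 33.3% |
| Baseline-adjusted | b × d | 0.3 × 0.1 = 0.03 | 0.7 × 0.5 = 0.35 | 0.03/1.5 = 2.0% to 0.35/1.5 = 23.3% |
| One-year score only | 0 | 0 | 0 | 0% |

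Section 4.6 also equates the target with 0.4 SD at an SD of 2.65, which is 0.4 × 2.65 = 1.06 points, not 1.5. On 1.06 the change-score range would be 0.1/1.06 = 9.4% to 0.5/1.06 = 47.2%. That inconsistency is a separate matter; it affects the percentages here, not the ordering.

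**The case against.** The strongest reply is that the order rests on one mark in an unreliable table. The table names ODI, which appears nowhere else in the documents. It omits WOMAC by name, miscounts visits, and runs physical therapy throughout enrolment although Section 4.7 describes 4 to 8 weeks. Section 4.8, read plainly, makes baseline the first thing done at entry. On this view the defect is an ambiguity to tidy up, not an adverse order. The table's faults are real, and WOMAC does reach week 0 only through Section 4.9. But the table is the only place that puts randomisation in time, and staff following it would randomise first. No other passage says otherwise.

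Second, harm to the primary result is not shown. The primary outcome is the one-year score, and Section 5 names neither a covariate nor a change score. Bias would require patients to learn their arm early, scores to shift by arm, and baseline to enter the analysis. This stands as a limit on the consequence: if one-year scores alone are compared, the baseline shift contributes nothing. Section 5 does not commit to that analysis, however.

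Third, the VAS problem is conditional, since a VAS may be taken within the screening check. That also stands; in that case only the wording needs repair.

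Fourth, a patient lost before week 0 would lack a one-year score under either order. True: an earlier baseline would add only the baseline value, for which Section 5 describes no use.

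**Conclusion.** The concern holds. As printed, randomisation precedes the first scheduled outcome measures by two weeks, WOMAC included through Section 4.9. No passage places baseline before allocation or withholds the arm until baseline is recorded.

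The size of any bias is unknown, and the ranges shown are illustrations under assumed inputs. The documents do not establish that patients learn their arm before week 0; the weakness is that nothing prevents it. The primary comparison is exposed only if change scores or baseline adjustment are used, which Section 5 leaves open. The eligibility consequence depends on which VAS the criterion means.

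Confidence is medium, because the table has other faults and may not reflect the intended order. The correction is worth making because it is cheap and removes a risk to self-reported measures in a trial whose patients are unblinded.

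**What to change.** Choose one of two orders:

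- Move the randomisation mark to week 0, after the eligibility VAS and all baseline measures including WOMAC are complete, and before device fitting.
- Move those measures to Screening, before randomisation.

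State the chosen order in Section 4.3, with the arm released only once baseline is recorded. In the inclusion criterion (Synopsis and Section 4.5), replace the reference to baseline with the named visit. Define entry in Section 4.8 and reconcile it with the Synopsis, which counts from the start of treatment. As a minor table correction, reconcile the VAS and ODI row with Section 4.9.

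The cost is a table edit, one sentence in Section 4.3 and small wording changes elsewhere. Sample size, alpha and power are unaffected. Under the first option, therapy slots are booked at shorter notice, and Section 1 says outpatient therapy capacity is limited. Under the second, the screening visit is longer and baseline may be up to two weeks old when treatment starts.

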4.9. Outcome measures

Primary study outcome:

- Western Ontario and McMaster Universities (WOMAC) pain scale at one year.
- WOMAC function scale at one year

Secondary study outcome: at: Pre-treatment, 4 weeks, 8 weeks, 12 weeks, 24 weeks, 52 weeks.

- WOMAC pain and function subscale
- PROMIS Pain Interference and Physical Function
- Costs: Assessment of total utilization and cost from resource utilization monitored via the CMO
- MOS item of the Short Form (SF)-36
- Spatio-temporal gait assessment including gait velocity, step length, single limb support and limb symmetry measured by Zeno Walkway ®
- 6-min walk test
- Blood pressure and resting heart rate

- Treatment adherence: Measured via attendance at sessions of therapy (conventional therapy), hours of use of AposTherapy (Patient to have step counter)
- Overall activity and sleep patterns (both arms (via FitBit Charge HR (<http://www.fitbit.com/chargehr#i.f9n1ye1ehxd30p>) motion sensor worn for one week after each evaluation session, mailed back via prepaid mailer at the end of the week.)

5. Statistical analysis

All demographic data will be reported as mean standard deviations and average. Data from primary and secondary outcome measures will be checked for skewness using Fisher-Pearson coefficient of skewness. ANOVA or Kuskal-Wallis test will be applied depending on normality of data. All statistical analysis will be conducted using IBM SPSS Statistics Ver.24.

6. Benefits

- Participants will all have physical therapy for their knee
- AposTherapy involves fewer visits to the physical therapy center thus allowing individuals more time at home and lower transportation costs
- AposTherapy is done at home and more convenient
- AposTherapy will be provided for free for participants.

7. Risks

- Muscle soreness associated with exercise
- Minimal fall risk with use of new footwear device and exercise

8. Subject Reimbursement

Participants will be reimbursed a total of \$40 at each assessment point (pre-treatment, at 4 weeks, 8 weeks, 12 weeks, 24 weeks and 52 weeks after entry into the study). Participants will

receive \$95 reimbursement for their time at the completion of the study after return of all devices and materials. This will apply to all arms of the study.

Study schedule:

Study Periods	Screening	1	2	3	4	5	6	7
Visit		1	2	3	4	5	6	7
Time (week)	-2	0	4	8	12	24	52	
Patient Information and Informed Consent	X							
Demographics	X							
Medical History	X							
In- /Exclusion Criteria	X							
Radiography	X							
Randomization	X							
Administer traditional physical therapy		Physical Therapy is administered according to the protocol for the duration of enrollment in the study						
Administer Biomechanical Device		X						
Adjustment Biomechanical Device			X	X	X	X		
VAS and ODI		X	X	X	X	X	X	
Secondary outcome measures		X	X	X	X	X	X	
Adverse Events		X	X	X	X	X	X	

Resources

AposTherapy	Montefiore

 • Training for Montefiore PTs • Full-time Apos resource to manage program on-site at Montefiore • AposTherapy devices 	
 • Clinical Principle Investigator Lead • Research staff – 2 coordinators • Data informatics, including patient population, demographics, historical costs, etc. • Research infrastructure including IRB, recruitment, clinical expertise • Study materials • Step counter/Fitbit monitors

Staff	Salary - Rate/Hr	Fringe	FTE or Hours	Total Cost
Attending Physician Supervision	\$165,000	30.5%	0.2	\$43,065
Study coordinator	\$0	0.0%	2	\$0
These will be Everest individuals				
Informatics costs	\$75		100	\$7,500
Biostatistical support	\$150		100	\$15,000
CMO staff support	\$65,000	30.5%	0.5	\$42,413
Total Staffing Cost				\$107,978
Materials	Cost per Unit	# of Patients	Qty	Subject Costs
Step counters:				
25% of Patients and 10% loss	\$50	37	41	\$2,050
Fitbit HR Monitors:				
25% of Patients	\$150	37	41	\$6,150
Mailing to Recover step counter/Fitbit:*	\$10	37		\$14,800

Transportation costs:	\$100	147		\$14,700
Subject Complete Reimbursement	\$100	147		\$14,700
Zeno Walkway	\$20,000		1	\$20,000
Total Materials				\$72,400
Total cost of the study				\$180,378

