The effect of AposTherapy on pain and function in Knee Osteoarthritis population.

A randomized controlled trial

Clinical Study Protocol

Study Type: Randomized controlled trial

PI

[name], MPH

Professor and Chairman of Rehabilitation Medicine

Albert Einstein College of Medicine

Chairman, Department of Rehabilitation Medicine

Montefiore Medical Center

Protocol Version and Date: Version 1.6, 12.20.2016

Study Synopsis	
Title of the study	The effect of AposTherapy on pain and function in Knee Osteoarthritis (OA) population. A randomized controlled trial
Study objective	To evaluate the effect of AposTherapy on pain and function in knee OA population.
Outcome measures	
Primary outcome measures:
 
 • Pain and function at 1-year post treatment initiation 
Secondary outcome measure:
 
 • Total healthcare utilization and costs of physical therapy and AposTherapy will be assessed, including physical therapy, ED visits, pharmacological pain treatments, injections, imaging studies, surgical procedures, physician visits related to knee pain and total physician visits • PROMIS Pain Interference and Physical Function • Pain medication consumption • Quality of life • Gait assessment • 6-min walk test • Blood pressure and resting heart rate • Adherence to treatment - AposTherapy (Patient to have step counter permanently attached to AposTherapy device, downloaded at each visit • Overall activity and sleep patterns, both groups. Will be measured via FitBit Charge HR

	
(http://www.fitbit.com/chargehr#i.f9n1ye1ehxd30p) motion sensor worn for one week after each evaluation session, mailed back via prepaid mailer at the end of the week.

Study design	A randomized controlled trial (AposTherapy compared to traditional physical therapy)
STUDY POPULATION	Patients suitable for inclusion in this study will be those fulfilling the following:

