Total number of patients	
One-hundred and forty-seven (147) individuals will be randomly assigned to one of two groups; traditional physical therapy or AposTherapy on a 1:2 ratio (49:98).
 
A sample size of 147 will yield 80% power to detect an expected difference on the WOMAC pain scale, with components measured on VAS scales from 0 to 10 and a summary score standardized to also range from 0 to 10, of 1.5 at a 2-sided alpha of 0.05. The difference corresponds to a clinically meaningful moderate effect size of 0.4 standard deviation units assuming a typical standard deviation of 2.65. Anticipating an attrition rate of 10%, we aim at recruiting 162 patients for the trial.

Study groups	
Patients will be randomly assigned to one of the following groups:
 
 • Patients with knee OA treated with AposTherapy • Patients with knee OA treated with traditional physical therapy
Assessment time points	
Patients will be enrolled in the study and have clinical evaluations at the following time points:
 
 • Pre-treatment • 4 weeks following treatment initiation

- 8 weeks following treatment initiation
- 12 weeks following treatment initiation
- 24 weeks following treatment initiation
- 52 weeks following treatment initiation

**The effect of AposTherapy on pain and function in Knee Osteoarthritis (OA) population. A
randomized controlled trial**

1. Background

AposTherapy is a home-based exercise program utilizing footwear that causes exercise with normal daily activity that may significantly improve function in patients with knee pain in general, and specifically knee osteoarthritis (OA). Capitalizing on the reported excellent adherence and clinical benefit of Apos Therapy in patients with significant lower limb arthritis, we propose to evaluate this as a conservative treatment that may supplant/supplement traditional pain medications and physical therapy in knee OA population. [3-6]

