A potential use of AposTherapy as a replacement for traditional physical therapy may yield a less costly, more effective therapy with better adherence. Problems with traditional therapy include poor patient adherence (patients often do not complete the sessions and have very poor adherence (about 50-60%) to home therapy programs [7]), added cost of travel (which may be more than \$100 per session for ambulette or access-a-ride for eligible patients), and the lack of continuation in an ongoing exercise program, leading to relapse and need for retreatment. Additionally, access to physical therapy is limited for many patients since there are not enough available outpatient therapy services to meet the needs of all patients. Finding an alternative exercise program that will increase adherence, decrease total therapy visits, and improve patient's outcomes with decreased dependence on pain medications is a high priority from both patient care and cost management perspectives.

AposTherapy potentially overcomes many of these issues with improving/modifying abnormal biomechanics (therefore decreasing pain), and a home-based exercise program utilizing footwear that causes exercise with normal activity by promoting perturbation. This biomechanical approach may significantly reduce pain and improve function in patients with

knee OA. Capitalizing on the reported excellent adherence and clinical benefit of AposTherapy in patients with significant knee OA, we propose to evaluate the biomechanical exercise (wearing an appropriately calibrated shoe at home for a prescribed amount of time each day) as a conservative treatment that may supplement or supplant traditional pain medications, interventional pain procedures and physical therapy in an at-risk urban inner city population with knee OA.

2. Study objective

The purpose of the current study is to evaluate the effect of this home-based biomechanical device and treatment (AposTherapy) in knee OA population. This will be a randomized single blinded (evaluator) trial of conventional physical therapy versus AposTherapy in patients with knee OA treated for one year.

In order to assess the efficacy of the intervention with AposTherapy on our patient population, a set of primary and secondary outcome measures will be defined:

3. Outcome measures

3.1. Primary outcome measures:

- Pain and function at 1 year following treatment initiation

3.2. Secondary outcome measure:

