4.6. Sample size

Our target recruitment is 147 individuals randomly assigned to one of two groups; traditional physical therapy or AposTherapy, on a 1:2 ratio. A sample size of 147 patients will yield 80% power to detect an expected difference on the WOMAC pain scale, with components measured on VAS scales from 0 to 10 and a summary score standardized to also range from 0 to 10, of 1.5 at a 2-sided alpha of 0.05. The difference corresponds to a

[figure not shown]
clinically meaningful moderate effect size of 0.4 standard deviation units assuming a typical standard deviation of 2.65. Anticipating an attrition rate of 10%, we aim at recruiting 162 patients for the trial (54 patients will be assigned to traditional physical therapy and 108 patients will be assigned to AposTherapy)

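### WOMAC pain and WOMAC function at one year are two unranked primary outcomes, with alpha and power stated for pain only and no testing order, alpha split or success rule

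*Combined protocol and SAP*

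**What the plan says.** The synopsis names as primary "Pain and function at 1-year post treatment initiation", and Section 3.1 repeats it as "Pain and function at 1 year following treatment initiation". Section 4.9 makes this specific with two bullets under one primary heading: "Western Ontario and McMaster Universities (WOMAC) pain scale at one year" and "WOMAC function scale at one year". Pain comes first, but nothing says that the order carries meaning.

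The sample-size text concerns pain alone. The synopsis states: "A sample size of 147 will yield 80% power to detect an expected difference on the WOMAC pain scale". Section 4.6 repeats this, with a difference of 1.5 points, two-sided alpha 0.05, an SD of 2.65 and an effect described as 0.4 SD. Function has no alpha, effect size or power of its own.

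Section 5 treats all outcomes alike: "Data from primary and secondary outcome measures will be checked for skewness using Fisher-Pearson coefficient of skewness", and then "ANOVA or Kuskal-Wallis test will be applied depending on normality of data". It does not mention multiplicity.

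Two other entries bear on which result is primary. The secondary list in Section 4.9 again includes the WOMAC pain and function subscales, and its time points include 52 weeks, so the same one-year scores are both primary and secondary. The study schedule has a VAS and ODI row separate from the row for secondary outcomes, and no WOMAC row.

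**The concern.** With two primary outcomes and one alpha, the plan has to say what counts as success. There are three usual answers: either outcome suffices, both are required, or one is tested before the other. They have different false-positive rates and different power, and this plan chooses none of them.

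If a significant result on either outcome at 0.05 were taken as a primary success, the chance of a false claim would exceed 5%. If both had to succeed, the error would be controlled, but the power figure for pain would no longer describe the chance of success. With no rule fixed in advance, the reading could be chosen once the results are known.

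**Working it through.** **Inputs from the documents.** Two-sided alpha 0.05; difference 1.5; SD 2.65; effect also given as 0.4 SD; 49 on physical therapy and 98 on AposTherapy; stated power 80% (synopsis and Section 4.6).

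**Assumptions.** The documents give neither the correlation between the two tests nor an effect on function. I take correlations from 0 to 0.95 for the error and 0 to 0.9 for power. A high value is plausible, because both scores come from one questionnaire in the same patients. For joint power I assume the same standardised effect on function as on pain. The two test statistics are treated as bivariate normal with critical value c = 1.96.

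**Step 1: the plan's own power for pain.** The standard error in SD units is sqrt(1/49 + 1/98) = 0.175.

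- 1.5/2.65 = 0.566 SD. Mean z = 0.566/0.175 = 3.235; power = Φ(3.235 − 1.96) = 89.9%.
- 0.4 SD (0.4 × 2.65 = 1.06 points). Mean z = 2.286; power = Φ(2.286 − 1.96) = 62.8%.

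The stated 80% is not reproduced by either input, and 1.5/2.65 is not 0.4. Both effect sizes are therefore carried forward.

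**Step 2: error if either outcome suffices.** With no true effect on either outcome, the two-sided error is 1 − P(|Z1| < c and |Z2| < c). Counting only results that favour AposTherapy, it is 1 − P(Z1 < c and Z2 < c).

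| Correlation | Two-sided | Favouring AposTherapy only |
|---|---|---|
| 0 | 9.75% | 4.9% |
| 0.5 | 9.1% | 4.5% |
| 0.7 | 8.4% | 4.2% |
| 0.9 | 7.0% | 3.5% |
| 0.95 | 6.5% | 3.2% |

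The reference values for a single test are 5% and 2.5%. At correlation 0 the two-sided figure is 1 − 0.95² = 9.75%. As the correlation tends to 1, it tends to 5%.

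**Step 3: error and power if both are required.** The error cannot exceed 5%: if one outcome has a real effect, a false joint success still needs a false positive on the other. Joint power is P(Z1 > c and Z2 > c).

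| Correlation | 0.566 SD | 0.4 SD | Each outcome at the stated 80% |
|---|---|---|---|
| 0 | 80.8% | 39.4% | 64.0% |
| 0.5 | 83.1% | 47.1% | 68.7% |
| 0.7 | 84.5% | 50.8% | 71.3% |
| 0.9 | 86.8% | 56.0% | 75.0% |

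Joint power stays above 80% only on the 0.566 SD reading.

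**Step 4: what a pain-first order gives up.** The chance that function is significant and pain is not equals single power minus joint power.

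- 0.566 SD: 89.9% − 80.8% = 9.1% at correlation 0, falling to 3.1% at 0.9.
- 0.4 SD: 62.8% − 39.4% = 23.4% at correlation 0, falling to 6.8% at 0.9.

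**Step 5: what it costs to let either suffice with control.** A split at 0.025 each (c = 2.241) lowers pain power to 84.0% (0.566 SD) or 51.8% (0.4 SD). Holm declares pain significant if Z1 > 2.241, or if Z1 > 1.96 and Z2 > 2.241. Pain power is then about 87% to 89% (0.566 SD) or 56% to 57% (0.4 SD) at correlations 0.9 to 0. Holm also holds the error at 5% and loses less.

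**The case against.** The best defence is that the plan can be read so that no inflation arises. The synopsis and Section 3.1 join pain and function with the word and, which can mean that both must succeed. Pain is also listed first and the trial is sized on it, which may suggest that pain leads. And a high correlation between two scores from one questionnaire brings the error closer to 5%.

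Most of this stands as a limit on the point. A reader might infer that the outcomes are equal in standing, or that the plan lets either one carry the claim. The documents support neither: they leave the outcomes unranked and adopt no success rule. The either-suffices reading is not excluded, but it is not chosen. A reader might also take 9.75% as the trial's error rate. That figure needs both the either-suffices reading and uncorrelated tests.

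The defence does not close the gap. Sizing on pain is not a testing order, and function keeps its primary label. The word and is not a success rule, and if both are required, no joint power has been given. Even at correlation 0.95 the either-suffices error is 6.5%.

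A fair objection to the remedy is that pain-first demotes an outcome that the protocol calls primary. That is so. It is recommended because it fits the existing sizing; it is not the only valid choice.

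**Conclusion.** The point holds as an ambiguity in the primary claim, and it is cheap to remove. The plan has two unranked primary outcomes, alpha and power for one of them, and no order, split or success rule.

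Its size depends on a reading that the documents do not settle. If either suffices, the two-sided error is 9.75% to 6.5% at assumed correlations 0 to 0.95; counting only results favouring AposTherapy, it is 4.9% to 3.5% at correlations 0 to 0.9, against 2.5%. If both are required there is no inflation, and the gap is the unstated joint power: 81% to 87% or 39% to 56%, according to which of the plan's two effect sizes is meant and assuming the same effect on function. The documents do not show that the trial runs at an inflated error. They show that nothing in the plan prevents it.

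The mismatch in the stated 80% power is a separate error, and this conclusion does not rest on it.

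**What to change.** Before outcome data by group are seen:

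1. State in Sections 4.9 and 5: *WOMAC pain at one year is tested first at two-sided 0.05; WOMAC function at one year is tested at two-sided 0.05 only if pain is significant.* This controls the error across the two primary tests, provided each test is itself valid at 0.05. The pain test is unchanged.
2. Limit the secondary WOMAC entry in Section 4.9 to time points before 52 weeks, so that a one-year score is not both primary and secondary.
3. Reconcile the VAS and ODI row of the study schedule with the WOMAC primary outcomes.
4. If the sponsor means either outcome to suffice, say so and use Holm rather than a plain 0.025 split. If both are required, say so and restate joint power, which needs an assumed effect on function that the documents do not give.
5. As a separate correction, settle whether the effect is 1.5 points or 0.4 SD, and restate the power in Section 4.6 and the synopsis: 89.9% or 62.8% at 49:98.

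The cost is a few lines of text and no new data. The downside of pain-first is that function cannot be claimed as a primary success when pain fails, which step 4 of the working puts at 3.1% to 9.1% of trials (0.566 SD) or 6.8% to 23.4% (0.4 SD). The documents do not give the trial's status; if data by group have already been seen, the rule should be reported as set afterwards.
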